10.53 Case Report Forms - Academic and Community Cancer Research United (ACCRU)

Submit the following AEs not specified in Section 10.5 (paper or electronic, as applicable)

10.531 Grade 2 AEs deemed *possibly, probably, or definitely* related to the study treatment or procedure.

10.532 Grade 3 and 4 AEs regardless of attribution to the study treatment or procedure.

10.533 Grade 5 AEs (Deaths)

10.5331 Any death within 30 days of the patient's last study treatment or procedure regardless of attribution to the study treatment or procedure.

10.5332 Any death more than 30 days after the patient's last study treatment or procedure that is felt to be at least possibly treatment related must also be submitted as a Grade 5 AE, with a CTCAE type and attribution assigned.

10.54 Late Occurring Adverse Events

Refer to the instructions in the Forms Packet (or electronic data entry screens, as applicable) regarding the submission of late occurring AEs following completion of the Active Monitoring Phase (i.e., compliance with Test Schedule in Section 4.0).

11.0 Treatment Evaluation

NOTE: This study uses protocol RECIST v1.1 template dated 2/16/2011. See the footnote for the table regarding measurable disease in Section 11.44, as it pertains to data collection and analysis.

Response and progression will be evaluated in this study using the international criteria proposed by the revised Response Evaluation Criteria in Solid Tumors (RECIST) guidelines (version 1.1)¹. Changes in the largest diameter (unidimensional measurement) of the tumor lesions and the short axis measurements in the case of lymph nodes are used in the RECIST guideline. Evaluations will be performed by the investigator at the times of treatment.

11.1 Schedule of Evaluations: For the purposes of this study, patients should be reevaluated every 12 weeks (i.e. 4 cycles),

11.2 Definitions of Measurable and Non-Measurable Disease

11.21 Measurable Disease

11.211 A non-nodal lesion is considered measurable if its longest diameter can be accurately measured as ≥ 2.0 cm with chest x-ray, or as ≥ 1.0 cm with CT scan, CT component of a PET/CT, or MRI.

11.212 A superficial non-nodal lesion is measurable if its longest diameter is ≥ 1.0 cm in diameter as assessed using calipers (e.g. skin nodules) or imaging. In the case of skin lesions, documentation by color photography, including a ruler to estimate the size of the lesion, is recommended.

11.213 A malignant lymph node is considered measurable if its short axis is ≥ 1.5 cm when assessed by CT scan (CT scan slice thickness recommended to be no greater than 5 mm).

Note: Tumor lesions in a previously irradiated area are not considered measurable disease.

11.22 Non-Measurable Disease

11.221 All other lesions (or sites of disease) are considered non-measurable disease, including pathological nodes (those with a short axis ≥ 1.0 to < 1.5 cm). Bone lesions, leptomeningeal disease, ascites, pleural/pericardial effusions, lymphangitis cutis/pulmonis, inflammatory breast disease, and abdominal masses (not followed by CT or MRI), are considered as non-measurable as well.

Note: 'Cystic lesions' thought to represent cystic metastases can be considered as measurable lesions, if they meet the definition of measurability described above. However, if non-cystic lesions are present in the same patient, these are preferred for selection as target lesions. In addition, lymph nodes that have a short axis <1.0 cm are considered non-pathological (i.e., normal) and should not be recorded or followed.

11.3 Guidelines for Evaluation of Measurable Disease

11.31 Measurement Methods:

- All measurements should be recorded in metric notation (i.e., decimal fractions of centimeters) using a ruler or calipers.
- The same method of assessment and the same technique must be used to characterize each identified and reported lesion at baseline and during follow-up. For patients having only lesions measuring at least 1 cm to less than 2 cm must use CT imaging for both pre- and post-treatment tumor assessments.
- Imaging-based evaluation is preferred to evaluation by clinical examination when both methods have been used at the same evaluation to assess the antitumor effect of a treatment.

11.32 Acceptable Modalities for Measurable Disease:

- Conventional CT and MRI: This guideline has defined measurability of lesions on CT scan based on the assumption that CT slice thickness is 5 mm or less. If CT scans have slice thickness greater than 5 mm, the minimum size for a measurable lesion should be twice the slice thickness.
- As with CT, if an MRI is performed, the technical specifications of the scanning sequences used should be optimized for the evaluation of the type and site of disease. The lesions should be measured on the same pulse sequence. Ideally, the same type of scanner should be used and the image acquisition protocol should be followed as closely as possible to prior scans. Body scans should be performed with breath-hold scanning techniques, if possible.
- PET-CT: If the site can document that the CT performed as part of a PET-CT is of identical diagnostic quality to a diagnostic CT (with IV and oral contrast), then the CT portion of the PET-CT can be used for RECIST measurements and can be used interchangeably with conventional CT in accurately measuring cancer lesions over time.
- Physical Examination: For superficial non-nodal lesions, physical examination is acceptable, but imaging is preferable, if both can be done. In the case of skin lesions, documentation by color photography, including a ruler to estimate the size of the lesion, is recommended.
- FDG-PET: FDG-PET scanning is allowed to complement CT scanning in assessment of progressive disease [PD] and particularly possible 'new' disease. A 'positive' FDG-PET scanned lesion is defined as one which is FDG avid with an update greater than twice that of the surrounding tissue on the

attenuation corrected image; otherwise, an FDG-PET scanned lesion is considered ‘negative.’ New lesions on the basis of FDG-PET imaging can be identified according to the following algorithm:

- a. Negative FDG-PET at baseline with a positive FDG-PET at follow-up is a sign of PD based on a new lesion.
- b. No FDG-PET at baseline and a positive FDG-PET at follow-up:
 - i. If the positive FDG-PET at follow-up corresponds to a new site of disease confirmed by CT, this is PD.
 - ii. If the positive FDG-PET at follow-up is not confirmed as a new site of disease on CT at the same evaluation, additional follow-up CT scans (i.e., additional follow-up scans at least 4 weeks later) are needed to determine if there is truly progression occurring at that site. In this situation, the date of PD will be the date of the initial abnormal FDG-PET scan.
 - iii. If the positive FDG-PET at follow-up corresponds to a pre-existing site of disease on CT that is not progressing on the basis of the anatomic images, it is not classified as PD.

11.33 Measurement at Follow-up Evaluation:

- A subsequent scan must be obtained at least four weeks following initial documentation of an objective status of either complete response (CR) or partial response (PR).
- In the case of stable disease (SD), follow-up measurements must have met the SD criteria at least once after study entry at a minimum interval of 6 weeks (see Section 11.44).
- The cytological confirmation of the neoplastic origin of any effusion that appears or worsens during treatment when the measurable tumor has met criteria for response or stable disease is mandatory to differentiate between response or stable disease (an effusion may be a side effect of the treatment) and progressive disease.
- Cytologic and histologic techniques can be used to differentiate between PR and CR in rare cases (e.g., residual lesions in tumor types such as germ cell tumors, where known residual benign tumors can remain.)

11.4 Measurement of Effect

11.41 Target Lesions & Target Lymph Nodes

- Measurable lesions (as defined in Section 11.21) up to a maximum of 5 lesions, representative of all involved organs, should be identified as “Target Lesions” and recorded and measured at baseline. These lesions can be non-nodal or nodal (as defined in 11.21), where no more than 2 lesions are from the same organ and no more than 2 malignant nodal lesions are selected.

Note: If fewer than 5 target lesions and target lymph nodes are identified (as there often will be), there is no reason to perform additional studies beyond those specified in the protocol to discover new lesions.

- Target lesions and target lymph nodes should be selected on the basis of their size, be representative of all involved sites of disease, but in addition should be those that lend themselves to reproducible repeated measurements. It may be the case that, on occasion, the largest lesion (or malignant lymph node) does not lend itself to reproducible measurements in which circumstance the next largest lesion (or malignant lymph node) which can be measured reproducibly should be selected.
- Baseline Sum of Dimensions (BSD): A sum of the longest diameter for all target lesions plus the sum of the short axis of all the target lymph nodes will be calculated and reported as the baseline sum of dimensions (BSD). The BSD will be used as reference to further characterize any objective tumor response in the measurable dimension of the disease.
- Post-Baseline Sum of the Dimensions (PBSD): A sum of the longest diameter for all target lesions plus the sum of the short axis of all the target lymph nodes will be calculated and reported as the post-baseline sum of dimensions (PBSD). If the radiologist is able to provide an actual measure for the target lesion (or target lymph node), that should be recorded, even if it is below 0.5 cm. If the target lesion (or target lymph node) is believed to be present and is faintly seen but too small to measure, a default value of 0.5 cm should be assigned. If it is the opinion of the radiologist that the target lesion or target lymph node has likely disappeared, the measurement should be recorded as 0 cm.
- Minimum sum of the dimensions (MSD): The minimum of the BSD and the PBSD.
- Sum of Perpendicular Diameters: The sum of the products of the two largest perpendicular diameters of a lesion will be calculated and reported. The SPD will be used to calculate the total measurable tumor burden per irRC assessment.
- Total Measurable Tumor Burden: per the irRC, all index and measurable new lesions are taken into account. The SPD of the two largest index lesions (five lesions per organ, up to 10 visceral lesions) is calculated at baseline and at each subsequent reassessment. The SPD of new, measurable lesions ($>5 \times 5$ mm; up to five new lesions per organ, 10 total visceral lesions) are added together for the total tumor burden.

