11.43 Response Criteria

11.431 All target lesions and target lymph nodes followed by CT/MRI/PET-CT/Chest X-ray/physical examination must be measured on re-evaluation at evaluation times specified in Section 11.1. Specifically, a change in objective status to either a PR or CR cannot be done without re-measuring target lesions and target lymph nodes.

Note: Non-target lesions and non-target lymph nodes should be evaluated at each assessment, especially in the case of first response or confirmation of response. In selected circumstances, certain non-target organs may be evaluated less frequently. For example, bone scans may need to be repeated only when complete response is identified in target disease or when progression in bone is suspected.

11.432 Evaluation of Target Lesions

Target lesions will be assessed using RECIST criteria for all primary endpoints (see **table below**).

Response Criteria per RECIST 1.1

	RECIST 1.1*
Complete Response (CR)	Disappearance of all target lesions AND each target lymph node must have short-axis reduction to <1.0 cm
Partial Response (PR)	At least 30% decrease in PBSD (sum of the longest diameter for all target lesions plus the sum of the short axis of all the target lymph nodes at current evaluation) taking the BSD as reference (see Section 11.41).
Progression (PD)	At least one of the following must be true: 
 At least one new malignant lesion, which also includes any lymph node that was normal at baseline (< 1.0 cm short axis) and increased to \geq 1.0 cm short axis during follow-up At least a 20% increase in PBSD (sum of the longest diameter for all target lesions plus the sum of the short axis of all the target lymph nodes at current evaluation) taking as reference the MSD (Section 11.41). In addition, the PBSD must also demonstrate an absolute increase of at least 0.5 cm from the MSD. See Section 11.32 for details in regards to the requirements for PD via FDG-PET imaging
Stable Disease (SD)	Neither sufficient shrinkage to qualify for PR, nor sufficient increase to qualify for PD taking as reference the MSD.

*Primary endpoint.

**Secondary endpoint. Tumor burden includes index, non-index, and emerging lesions while on therapy.

11.433 Evaluation of Non-Target Lesions & Non-target Lymph Nodes

- Complete Response (CR): All of the following must be true:
 - a. Disappearance of all non-target lesions.
 - b. Each non-target lymph node must have a reduction in short axis to <1.0 cm.

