16.2 Primary Endpoint

This study will assess the confirmed response rate associated with MK-3475/Pembrolizumab in small bowel adenocarcinoma. Confirmed response rate will be defined as meeting RECIST 1.1 criteria on two consecutive evaluations at least 4 weeks apart. Confirmed response will be evaluated using the first year of treatment (first 18 cycles of treatment). All patients meeting the eligibility criteria who have a signed consent form and have begun treatment will be evaluable for response.

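### The progression reference sum (MSD), read as written, leaves out earlier post-baseline sums, so target-lesion progression after shrinkage would be called late; the running minimum that is probably intended is not stated

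*Combined protocol and SAP*

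**What the plan says.** Section 11.41 defines three sums. The BSD is the baseline sum. The later sum of the same lesions "will be calculated and reported as the post-baseline sum of dimensions (PBSD"), with no statement of which visit or visits are meant. The third is given in a single line: "Minimum sum of the dimensions (MSD): The minimum of the BSD and the PBSD".

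The RECIST 1.1 table in section 11.432 uses these sums with two different references. PR requires "At least 30% decrease in PBSD", measured against the BSD. PD requires "At least a 20% increase in PBSD", where the PBSD is explained as the sum of target-lesion diameters plus the "short axis of all the target lymph nodes at current evaluation) taking as reference the MSD (Section 11.41"). PD also has an absolute condition: "the PBSD must also demonstrate an absolute increase of at least 0.5 cm from the MSD". SD is what remains, again with the MSD as reference.

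Both main efficacy analyses depend on this table. In section 16.2, "Confirmed response rate will be defined as meeting RECIST 1.1 criteria on two consecutive evaluations at least 4 weeks apart". Section 16.6 determines progression for PFS by RECIST 1.1, and the note under the table in section 11.44 dates progression from the first visit that meets standard RECIST 1.1.

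**The concern.** The PD row explains the PBSD as the current sum, and the MSD is the smaller of the BSD and the PBSD. Put together, the current sum is compared with a minimum that already contains it. Nothing brings in the sums from earlier post-baseline visits, so a tumor that shrinks and then regrows has no recorded low point to be measured from.

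Two results are exposed. PFS would be too long in patients who shrink first and then progress in target lesions. A scan that shows substantial regrowth could also serve as the second, confirming PR for the primary endpoint. Section 11.0 has investigators make the evaluations in a multicenter trial, so each site has to interpret the line, and section 16 gives no derivation that would override it. The trial has a single arm, so no control group shares the same error.

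**Working it through.** **The plan's own figure.** Section 16.32 declares activity with 7 or more confirmed responses in 35. The exact binomial tail P(X ≥ 7 | n = 35) is 0.0552 at p = 0.10 and 0.9350 at p = 0.30. These agree with the 0.06 and 94% in section 16.33 at the rounding given there. The calculation takes the confirmed response rate as an input, so alpha, power and N are the same under either reading of the MSD.

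**Inputs.** PD: at least 20% and at least 0.5 cm above the MSD. PR: at least 30% below the BSD (both 11.432). Scans every 12 weeks (11.1).

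**Two readings**, with S the sum at the visit being assessed:

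- Literal: MSD = min(BSD, S).
- Running minimum: MSD = min(BSD, all earlier post-baseline sums).

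Under the literal reading, if S ≤ BSD then MSD = S and the increase is (S − S)/S = 0%, so PD is impossible. If S > BSD then MSD = BSD and PD needs S ≥ 1.2 × BSD.

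**Regrowth needed after shrinkage s.** Literal: 1.2/(1 − s) − 1. Running minimum: 20%, which is reached at 1.2 × (1 − s) of baseline.

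| Shrinkage at nadir | Regrowth from nadir, literal | Literal PD at | Running-minimum PD at |
|---|---|---|---|
| 30% | 1.2/0.7 − 1 = 71% | 120% of baseline | 84% of baseline |
| 50% | 1.2/0.5 − 1 = 140% | 120% | 60% |
| 70% | 1.2/0.3 − 1 = 300% | 120% | 36% |

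These percentages assume reference sums of at least 0.5/0.20 = 2.5 cm. Below that size the 0.5 cm condition governs.

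**Worked sequences, BSD 10.0 cm.**

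| Later sums (cm) | Change at last scan | Literal | Running minimum |
|---|---|---|---|
| 5.0, 8.0 | (8.0 − 5.0)/5.0 = +60% from nadir | PR, SD | PR, PD |
| 3.0, 6.5 | (6.5 − 3.0)/3.0 = +117% from nadir; 35% below baseline | PR, PR (confirmed) | PR, PD |
| 5.8, 7.0 | (7.0 − 5.8)/5.8 = +21% from nadir; 30% below baseline | PR, PR (confirmed) | PR, PD |
| 11.0, 12.0 | +20% from baseline; never below baseline | SD, PD | SD, PD |

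In the second and third rows the last sum meets both the PR test (against BSD) and the running-minimum PD test. Section 11.432 does not say which prevails; the table above lets PD prevail.

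**When the confirming scan is affected.** The second sum must be at most 0.70 × BSD and at least 1.2 times the first sum. The first sum must therefore be at most 0.70/1.2 = 58.3% of BSD, a shrinkage of at least 41.7%. The regrowth must also reach 0.5 cm.

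**Illustrative PFS delay.** Assume exponential regrowth with the sum doubling in 60 to 120 days (not in the documents). The delay is the doubling time × log2(1/(1 − s)): 31 to 62 days after 30% shrinkage and 60 to 120 days after 50%. Against an 84-day scan interval that is about 0.4 to 1.4 intervals.

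**Illustrative effect on the decision.** If such cases raised a true 10% confirmed rate to 11% or 12% (assumed), P(X ≥ 7 | 35) would be 0.083 or 0.119. Nothing in the documents indicates that the shift would be that large.

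**The case against.** The strongest reply is that the literal reading cannot be what was meant. The definition in 11.41 does not itself contain the word current; that comes from the PD row, where it describes the sum under test. The table deliberately uses the BSD for PR and a separately named minimum for PD, and that minimum has no function unless it runs over earlier visits. Sections 11.0, 11.44, 16.2 and 16.6 all point to RECIST 1.1. This stands as evidence of intent. It does not repair the text: the table headed as RECIST 1.1 is the operative rule, and no section says that earlier sums enter the minimum.

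Stronger readings are tempting, and the documents do not support them:

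- A reader might infer that the sponsor chose baseline as the progression reference. Nothing shows such a choice, and the two-reference table argues against it.
- A reader might infer a proven departure from RECIST 1.1. Its rule on the reference sum is not reproduced in the protocol; what can be shown is that 11.41 and 11.432 together do not deliver a working minimum.
- A reader might infer that every patient who shrinks and regrows is misclassified, or only responders. Neither is so. Patients who reach 120% of baseline are PD, and regrowth under 20% or 0.5 cm is not PD on either reading. New lesions, clear non-target progression, the FDG-PET rules and symptomatic deterioration do not use the MSD. Patients with less than 30% shrinkage can be affected too.
- A reader might infer that the primary result is in jeopardy because 6 versus 7 of 35 decides it. That is true of any cutoff and says nothing about how often the narrow confirming-scan case occurs.

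**Conclusion.** The concern holds as a wording error in an endpoint-defining formula, of moderate severity. Followed literally, the formula delays target-lesion PD in patients who first fall below baseline and then progress by target lesions alone, and so lengthens PFS. Its effect on confirmed response is possible but confined to the case derived above, with unknown frequency.

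The conclusion rests on reading 11.41 together with the PD row of 11.432. If the case report form or the analysis program already takes the minimum over earlier visits, the harm is limited to ambiguous text. The documents do not show whether it does. The delay in days and the shifted response rates are illustrations under stated assumptions, not estimates for this trial.

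**What to change.** 1. In 11.41, define the PBSD as the sum at the current evaluation, and the MSD as the smallest sum recorded before the current evaluation, that is, the minimum of the BSD and all earlier PBSDs (nadir).
2. In 11.432, state that a sum meeting both PR against the BSD and PD against the MSD is PD.
3. Before response and PFS are analysed, verify that the RECIST measurement form and the analysis derivation use this nadir, and re-derive any status that does not.

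The cost is a few sentences and one check of the derivation. No patients, scans or procedures are added, and the design calculations stay as they are. The downside is that PFS and response may look slightly less favourable than under the literal rule.

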11.42 Non-Target Lesions & Non-Target Lymph Nodes

Non-measurable sites of disease (Section 11.22) are classified as non- target lesions or non-target lymph nodes and should also be recorded at baseline. These lesions and lymph nodes should be followed in accord with 11.433.

11.43 Response Criteria

11.431 All target lesions and target lymph nodes followed by CT/MRI/PET-CT/Chest X-ray/physical examination must be measured on re-evaluation at evaluation times specified in Section 11.1. Specifically, a change in objective status to either a PR or CR cannot be done without re-measuring target lesions and target lymph nodes.

Note: Non-target lesions and non-target lymph nodes should be evaluated at each assessment, especially in the case of first response or confirmation of response. In selected circumstances, certain non-target organs may be evaluated less frequently. For example, bone scans may need to be repeated only when complete response is identified in target disease or when progression in bone is suspected.

11.432 Evaluation of Target Lesions

Target lesions will be assessed using RECIST criteria for all primary endpoints (see **table below**).

Response Criteria per RECIST 1.1

	RECIST 1.1*
Complete Response (CR)	Disappearance of all target lesions AND each target lymph node must have short-axis reduction to <1.0 cm
Partial Response (PR)	At least 30% decrease in PBSD (sum of the longest diameter for all target lesions plus the sum of the short axis of all the target lymph nodes at current evaluation) taking the BSD as reference (see Section 11.41).
Progression (PD)	At least one of the following must be true: 
 At least one new malignant lesion, which also includes any lymph node that was normal at baseline (< 1.0 cm short axis) and increased to \geq 1.0 cm short axis during follow-up At least a 20% increase in PBSD (sum of the longest diameter for all target lesions plus the sum of the short axis of all the target lymph nodes at current evaluation) taking as reference the MSD (Section 11.41). In addition, the PBSD must also demonstrate an absolute increase of at least 0.5 cm from the MSD. See Section 11.32 for details in regards to the requirements for PD via FDG-PET imaging
Stable Disease (SD)	Neither sufficient shrinkage to qualify for PR, nor sufficient increase to qualify for PD taking as reference the MSD.

*Primary endpoint.

**Secondary endpoint. Tumor burden includes index, non-index, and emerging lesions while on therapy.

11.433 Evaluation of Non-Target Lesions & Non-target Lymph Nodes

- Complete Response (CR): All of the following must be true:
 - a. Disappearance of all non-target lesions.
 - b. Each non-target lymph node must have a reduction in short axis to <1.0 cm.
- Non-CR/Non-PD: Persistence of one or more non-target lesions or non-target lymph nodes.
- Progression (PD): At least one of the following must be true:
 - a. At least one new malignant lesion, which also includes any lymph node that was normal at baseline (< 1.0 cm short axis) and increased to ≥ 1.0 cm short axis during follow-up.
 - b. Unequivocal progression of existing non-target lesions and non-target lymph nodes. (NOTE: Unequivocal progression should not normally trump target lesion and target lymph node status. It must be representative of overall disease status change.)
 - c. See Section 11.32 for details in regards to the requirements for PD via FDG-PET imaging.

